6. ANALYSES AND SUMMARIES

6.1. Primary Endpoints

6.1.1. Percent Change from Baseline in EASI total score at Day 29

6.1.1.1. Main Analysis

- Estimand strategy: Hypothetical.
- Analysis set: FAS.
- Analysis methodology: percent change from baseline in EASI total score at Day 29, will be analyzed using MMRM that includes treatment group, visit, and treatment group-by-visit interaction as factors and baseline value as a covariate. Within-subject variability will be accounted for using a random effect with the first-order autoregressive (AR(1)) covariance matrix.
- Intercurrent events and missing data: data after treatment discontinuation prior to Day 29 will not be considered. Missing values will not be explicitly imputed and will be assumed to be MAR.
- Reporting results:
 - Tables: The sample size, least-squares (LS) mean of percent change from baseline and 95% CI for each treatment, LS mean of difference and the corresponding 95% CI, and p-value will be presented at Day 29.

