9. DATA ANALYSIS/STATISTICAL METHODS

Detailed methodology for summary and statistical analyses of the data collected in this study is outlined here and further detailed in a statistical analysis plan (SAP), which will be maintained by the sponsor. The SAP may modify what is outlined in the protocol where appropriate; however, any major modifications of the primary endpoint definitions or their analyses will also be reflected in a protocol amendment.

Efficacy analyses will be performed on the Full Analysis Set (FAS) which includes all subjects who are randomized and dispensed investigational product. Analyses based on the Per Protocol Analysis Set (PPAS) will be considered supportive. The PPAS includes all subjects in the FAS who complete the Day 29 evaluation without any major protocol deviations. Safety analyses will be performed on the Safety Analysis Set (SAFETY) which includes all subjects who are randomized and received at least one confirmed dose of investigational product.

Major protocol deviations will be summarized. Noncompliance with investigational product administration requirement will be summarized in terms of number of applications, number of days dosing, amount of drug used, and compliant status. A subject will be considered compliant with the dosing regimen if the subject applies at least 80% but no more than 120% of the expected applications during the investigational product application period, and has not missed 6 or more consecutive doses.

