9.2. Efficacy Analysis

9.2.1. Analysis of the Primary Endpoint

The primary efficacy endpoint, percent change from baseline in EASI total score at Day 29, will be analyzed using a linear mixed-effect model for repeated measures that includes treatment group, visit, and treatment group by visit interaction as factors and baseline value as a covariate. Within-subject variability will be accounted for using a random effect with the first order autoregressive (AR(1)) covariance matrix.

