5.1. Hypotheses and Decision Rules

The study will be declared a success with crisaborole shown to be superior to vehicle with respect to the primary efficacy endpoint, percent change from baseline in EASI total score at Day 29, if the mean percent change in the Crisaborole arm is lower than that in the vehicle arm and the difference is statistically significant at the two-sided level of 0.05.

After crisaborole is shown to be superior to vehicle with respect to the primary efficacy endpoint, it will be compared with vehicle with respect to the key secondary efficacy endpoints using gate-keeping method.

After and only after crisaborole is shown to be superior to vehicle with respect to the percent change from baseline in EASI total score at Day 29, crisaborole will be declared superior to vehicle with respect to the improvement rate in ISGA at Day 29, i.e., the percentage of patients with ISGA score of Clear (0) or Almost Clear (1), at Day 29, if the rate in the crisaborole arm is higher than that in the vehicle arm and the difference is statistically significant at the two-sided level of 0.05.

After and only after crisaborole is shown to be superior to vehicle with respect to the improvement rate in ISGA at Day 29, crisaborole will be declared superior to vehicle with respect to the success rate in ISGA at Day 29, i.e., the percentage of patients with ISGA score of Clear (0) or Almost Clear (1) with at least a 2 grade improvement from Baseline, at Day 29, if the rate in the crisaborole arms is higher than that in the vehicle arm and the difference is statistically significant at the two-sided level of 0.05.

After and only after crisaborole is shown to be superior to vehicle with respect to the success rate in ISGA at Day 29, crisaborole will be declared superior to vehicle with respect to the change from baseline in Peak Pruritus NRS at Week 4 - for subjects ≥ 12 years, if the mean change of the crisaborole arm is lower (i.e., larger reduction) than that in the vehicle arm and the difference is statistically significant at the two-sided level of 0.05.

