5.2.2. Analyses for Continuous Endpoints

Continuous endpoints will be descriptively summarized using sample size, mean, standard deviation, median and range.

For the analysis in which missing values are not explicitly imputed, continuous endpoints will be analyzed using a linear Mixed effect Model for Repeated Measures (MMRM, [Mallinckrodt et al. 2001](#)) with treatment group, visit, and treatment group-by-visit interaction as factors and baseline value as a covariate. Within-subject variability will be accounted for using a random effect with the first-order autoregressive (AR(1)) covariance matrix if there are no convergence issues, otherwise other structures will be considered.

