6.1.1.2. Supplementary Analyses

An analysis using PPAS will be performed. It will use the same methodology and handling of intercurrent events as the main analysis.

6.1.2. TEAEs (including application site reactions) & SAEs and clinically significant changes in vital signs and clinical laboratory parameters

All safety analyses will be conducted on the Safety Analysis Set.

Pfizer standard will be utilized in reporting routine safety variables (Pfizer Safety Rulebook).

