9. APPENDICES

Appendix 1. Summary of Efficacy Analysis

Table1. List of primary and secondary efficacy analyses

Efficacy Endpoints	Analysis Set	Analysis Method	Missing Data Imputation	Primary Analysis Endpoints
Percent change from baseline in EASI total score at Day 29	FAS	MMRM (model includes Days 8, 15, 22, 29)	Data after treatment discontinuation will not be included, MMRM handles missing data.	Yes
Percent change from baseline in EASI total score at Day 29 (Supplementary)	PPAS	MMRM (model includes Days 8, 15, 22, 29)	Data after treatment discontinuation will not be included, MMRM handles missing data.	Yes
Achievement of Improvement in ISGA at Days 29	FAS	normal approximation to response rates	MI-MCMC	No
Achievement of Improvement in ISGA at Days 29 (Supportive)	FAS	normal approximation to response rates	NRI	No
Achievement of Improvement in ISGA at Days 29 (Supplementary)	PPAS	normal approximation to response rates	MI-MCMC	NO
Achievement of Success in ISGA at Day 29	FAS	Normal approximation to response rates	MI-MCMC	No
Achievement of Success in ISGA at Day 29 (Supportive)	FAS	Normal approximation to response rates	NRI	No
Achievement of Success in ISGA at Day 29 (Supplementary)	PPAS	Normal approximation to response rates	MI-MCMC	No

Table1. List of primary and secondary efficacy analyses

Efficacy Endpoints	Analysis Set	Analysis Method	Missing Data Imputation	Primary Analysis Endpoints
Change from Baseline in Peak Pruritus NRS at Week 4 – for subjects ≥ 12 years	FAS	MMRM (model includes Week 1, 2, 3, 4)	Data after treatment discontinuation will not be included, MMRM handles missing data.	No
Change from Baseline in Peak Pruritus NRS at Week 4 – for subjects ≥ 12 years (Supplementary)	PPAS	MMRM (model includes Week 1, 2, 3, 4)	Data after treatment discontinuation will not be included, MMRM handles missing data.	No
Success in ISGA over time	FAS	normal approximation to response rates	MI-MCMC	No
Improvement in ISGA over time	FAS	normal approximation to response rates	MI-MCMC	No
Percent Change from baseline in EASI total score over time	FAS	MMRM (model includes Days 8, 15, 22, 29)	MMRM handles missing data	No
Change from baseline in %BSA over time	FAS	MMRM (model includes Days 8, 15, 22, 29)	MMRM handles missing data	No
Achievement of EASI-50 over time	FAS	normal approximation to response rates	MI-MCMC	No
Achievement of EASI-75 over time	FAS	normal approximation to response rates	MI-MCMC	No

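### The primary EASI model fixes plain AR(1), which forces one variance on all four visits with no robust standard error or covariance sensitivity analysis, so the 0.05 level at Day 29 is not guaranteed

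*SAP*

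**What the plan says.** SAP 6.1.1.1 analyses percent change from baseline in EASI by MMRM, with treatment, visit, treatment-by-visit and baseline value in the mean model. On the covariance it says: "Within-subject variability will be accounted for using a random effect with the first-order autoregressive (AR(1)) covariance matrix". Protocol 9.2.1 says the same: "Within-subject variability will be accounted for using a random effect with the first order autoregressive (AR(1)) covariance matrix". SAP Appendix 1, Table 1 puts Days 8, 15, 22 and 29 in the model.

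Three other places bear on the point:

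- **SAP 5.2.2** is the only place that lets the analyst leave AR(1). It applies that "covariance matrix if there are no convergence issues, otherwise other structures will be considered". The alternatives are not named, and the trigger is non-convergence, not poor fit.
- **SAP 6.1.1.2** gives the one supplementary analysis of this endpoint, on the per-protocol set: "It will use the same methodology and handling of intercurrent events as the main analysis".
- **SAP 5.1** sets a two-sided 0.05 level and declares success "if the mean percent change in the Crisaborole arm is lower than that in the vehicle arm and the difference is statistically significant". The three key secondary endpoints are tested in sequence only after that.

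The key secondary Peak Pruritus NRS analysis (SAP 6.2.3.1, Protocol 9.2.2) uses the same covariance structure. Neither document mentions a sandwich variance, an unstructured or heterogeneous matrix, or a degrees-of-freedom method.

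**The concern.** Plain AR(1) has two parameters: one variance and one correlation that decays with lag. It allows no change in variance between visits. Reading the phrase about a random effect as a subject intercept plus AR(1) residuals does not help, because the total variance is still the same at every visit.

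With treatment-by-visit terms and complete data, the Day 29 contrast is essentially the difference in Day 29 means. Its model-based standard error, however, uses the single variance fitted over all four visits. The nominal level therefore holds only if the Day 29 variance is close to that fitted value. The plan neither argues this nor checks it.

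This one test decides whether the trial succeeds and whether any key secondary endpoint can be tested. If variance rises towards Day 29, type I error exceeds 5% and the confidence interval is too narrow. If it falls, the test is conservative and loses planned power. The two ISGA tests are affected only through their place in the sequence.

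**Working it through.** **Inputs from the documents.** 384 subjects, 256:128; 12-point difference; about 90% power; two-sided 0.05 (Protocol 9.1, SAP 5.1); four visits (SAP Appendix 1). The planning SD is not visible because the sample-size sentence runs into a redaction. No by-visit SDs are given.

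**Step 1: SD implied by the stated power.**
SD = 12 / [(1.960 + 1.282) × √(1/256 + 1/128)] = 12 / (3.242 × 0.10825) = 34.2.
This is back-solved with no dropout, so it is an assumption and not a document figure.

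**Step 2: what AR(1) fits when variances differ.** Let S be the true 4×4 covariance and R(ρ) the AR(1) correlation matrix. In large samples with complete data, the fit minimises log|R| + 4·log(tr(R⁻¹S)/4), and the fitted variance is tr(R⁻¹S)/4. Let k = fitted SD / true Day 29 SD. Then:

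- type I error = 2 × [1 − Φ(1.960 k)]
- power = Φ(3.242 − 1.960 k)

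**Step 3: assumed range.** Day 29 SD 34.2, SD linear over the four visits, true correlation AR(1) with ρ = 0.75.

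| Day 8 / Day 29 SD | k | Type I error | Power |
|---|---|---|---|
| 0.7 | 0.860 | 9.2% | 94.0% |
| 0.8 | 0.904 | 7.6% | 92.9% |
| 0.9 | 0.951 | 6.2% | 91.6% |
| 1.0 | 1.000 | 5.0% | 90.0% |
| 1.1 | 1.051 | 3.9% | 88.1% |
| 1.25 | 1.130 | 2.7% | 84.8% |
| 1.4 | 1.212 | 1.8% | 80.7% |

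Worked row, ratio 0.8: 1.960 × 0.904 = 1.772, and 2 × [1 − Φ(1.772)] = 7.6%. The extra power in the first three rows comes from the inflated level and is not a gain.

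Type I error stays within 4.5–5.5% only for ratios of about 0.96 to 1.05 on this path. Replacing the true correlation by AR(1) with ρ = 0.6 or 0.85, or by compound symmetry with 0.6 or 0.75, moves it by less than 0.1 point on this path. Unequal variance is what drives the result.

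**Step 4: off the linear path** (SDs at Days 8, 15, 22, 29; ρ = 0.75).

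- 30, 38, 34.2, 34.2: 5.5% (5.3–5.7% over the same correlations). The error can be small even when early visits differ.
- 27.4, then 34.2 throughout: 6.6%.
- 42.75, then 34.2 throughout: 3.2%.

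**Step 5: simulation.** With complete data and no baseline covariate (20,000 null and 8,000 alternative trials per ratio), ratios 0.7, 0.8, 0.9, 1.0, 1.1 and 1.25 gave:

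- AR(1) type I error: 9.3, 7.6, 6.4, 4.9, 4.0 and 2.8%
- AR(1) power: 94.3, 92.6, 91.4, 89.6, 88.4 and 84.8%
- Unstructured covariance: type I error 4.9–5.3% and power 89.7–90.3% throughout

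A separate REML simulation included a baseline covariate and 8–10% missing-at-random dropout by Day 29 (2,000 trials per scenario, Monte Carlo error about 0.5 point). Null rejection rates were:

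| Assumed SDs | AR(1), model SE | AR(1), sandwich SE | Unstructured |
|---|---|---|---|
| 34 at all visits | 5.3% | 5.5% | 5.2% |
| 25, 28, 31, 34 | 8.4% | 4.2% | 4.0% |

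**The case against.** The strongest reply is that size and direction are assumed throughout. No by-visit SD is visible, the linear path is a construction, and four of the seven ratios in the table give a nominal or conservative test. A type I error of 9.2% needs a Day 8 SD 30% below that at Day 29. All of this stands. It means the plan has a vulnerability; it does not show that this trial's test is inflated.

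A second reply is that a lighter remedy would do: keep AR(1) with a sandwich standard error, or add an unstructured sensitivity analysis. The dropout simulation supports the first (4.2% against 4.0%). The second leaves the primary analysis unchanged, so it should not need a protocol amendment, but it would not repair the test that decides success.

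Third, an unstructured matrix pooled over arms does not guarantee 5% either. With 2:1 allocation and an assumed vehicle/crisaborole SD ratio of 1.2, the pooled variance is (2 + 1.44)/3 = 1.147 in units of the crisaborole variance. The model variance of the difference is 1.147 × (1/256 + 1/128) = 0.01344, against a true 1/256 + 1.44/128 = 0.01516. That gives k = 0.942 and a type I error of 6.5%. A ratio of 1.3 gives 7.2%. This limit is real and separate from the visit-variance problem.

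Fourth, SAP 5.2.2 calls for descriptive standard deviations, so a large departure may be visible in the report. That helps a reader but does not control the error of the test. Prespecifying AR(1) prevents a data-driven choice of structure; it does not make the standard error right.

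**Conclusion.** The concern holds. Both documents fix a covariance structure that assumes equal variance at all four visits, and nothing in the visible text protects the Day 29 test if that assumption fails. For assumed Day 8/Day 29 SD ratios from 0.8 to 1.25 on a linear path, type I error runs from 7.6% down to 2.7%. At the upper end power falls to 84.8%. These figures rest on the back-solved SD of 34.2, complete data and equal arm variances. The direction in this trial cannot be known from the documents, and the error is near zero if the Day 29 variance happens to match the fitted value. No magnitude was computed for Peak Pruritus NRS, which shares the structure. The point should be fixed; confidence is medium because the by-visit variances are not available.

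**What to change.** In SAP 5.2.2, 6.1.1.1 and 6.2.3.1, and in Protocol 9.2.1 and 9.2.2:

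1. Make an unstructured covariance primary, with a stated degrees-of-freedom method.
2. Replace the open-ended convergence clause with a fixed order, for example heterogeneous Toeplitz, then heterogeneous AR(1), and require a sandwich variance for any structured fallback.
3. Keep AR(1) as a sensitivity analysis.

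**Cost.** Ten covariance parameters instead of two (three if the current wording means a random intercept plus AR(1)), which is feasible with about 384 subjects and four visits. In the simulations, power under equal variances was essentially unchanged. Because the primary analysis changes, Protocol 9 applies: "any major modifications of the primary endpoint definitions or their analyses will also be reflected in a protocol amendment".

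If the sponsor prefers to keep AR(1), the minimum that addresses the test itself is a sandwich standard error in the primary analysis, with an unstructured model as sensitivity analysis. A pooled unstructured matrix does not cover unequal variances between arms; if that is also to be covered, it needs its own provision.

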6.1.1.2. Supplementary Analyses

An analysis using PPAS will be performed. It will use the same methodology and handling of intercurrent events as the main analysis.

6.1.2. TEAEs (including application site reactions) & SAEs and clinically significant changes in vital signs and clinical laboratory parameters

All safety analyses will be conducted on the Safety Analysis Set.

Pfizer standard will be utilized in reporting routine safety variables (Pfizer Safety Rulebook).

6.2. Secondary Endpoints

6.2.1. Achievement of Improvement in ISGA at Day 29

6.2.1.1. Main Analysis

- Estimand strategy: Hypothetical.
- Analysis set: FAS.
- Analysis methodology: The percentage of subjects achieving Improvement in ISGA at Day 29 will be compared between crisaborole arm and vehicle arm and the difference will be tested based on normal approximation to response rates.
- Intercurrent events and missing data: Data after treatment discontinuation prior to Day 29 will not be considered. Missing ISGA scores will be derived for the analysis using MI-MCMC.
- Reporting results:
 - Tables: The sample size, number, percentage and 95% CI of percentage of subjects achieving Improvement in ISGA at Day 29 will be presented for each treatment. Risk difference and the corresponding 95% CI and p-value for the test of difference based on normal approximation to response rates will also be presented at Day 29.

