1.4. Rationale

1.4.1. Study and Dose Rationale

In this China and Japan study, a similar study design to the two global pivotal studies (AN2728-AD-301 and AN2728-AD-302) will be used to investigate the efficacy and safety of Crisaborole Ointment, 2% twice daily (BID) in Chinese and Japanese pediatric and adult subjects (ages 2 years and older) with mild to moderate AD, to support the registration of Crisaborole in China and Japan.

Dose selection for the global pivotal clinical studies was based on safety and efficacy results from Phase 2 studies, and the dose selected was later confirmed to be safe and effective for commercialization by the results of the Phase 3 studies.

Phase 2 Study AN2728-AD-204 compared two concentrations of crisaborole (2% and 0.5%) applied QD or BID in adolescents with mild to moderate AD. The largest dose-related response and the greatest improvement in all 5 component signs and symptoms of AD occurred in the crisaborole 2% BID group, with a notable reduction from baseline in the pruritus score.

The 2% dosage strength of the crisaborole ointment formulation administered BID was selected for study in Phase 3 as the highest well-tolerated dose to maximize the potential for efficacy with minimal safety risk. Results from the Phase 3 trials in which subjects aged 2 years and older with mild to moderate AD were dosed BID for 28 days with Crisaborole

Ointment, 2% confirm the safety and efficacy of this formulation strength and dosing regimen in subjects with mild to moderate AD (AN2728-AD-301, AN2728-AD-302).

Long-term (up to 12 months) intermittent use in this patient population was shown to be safe in a 48-week long-term safety study (AN2728-AD-303).

The safety of the 2% dosage strength was confirmed in additional studies, including maximal use systemic exposure (MUSE) studies (pediatric subjects with AD and adult subjects with psoriasis) and with supra-therapeutic dosing in a TQT study (healthy adult subjects). In the pooled Phase 3 registration studies, higher rates of success in ISGA at Day 29 were observed in the crisaborole group than in the vehicle group for the subgroups of sex, age, race, and ethnicity. The proportion of Asian subjects is around 5%, similar trend was observed in the Asian subgroup of the pooled global pivotal studies, with a success in ISGA of 17.3% in the crisaborole group and 11.1% in the vehicle group. The safety profile of crisaborole was not affected by age, sex, ethnicity, or race.

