4.1. Inclusion Criteria

Subjects must meet all of the following inclusion criteria to be eligible for enrollment into the study:

1. Is male or female and the appropriate age in years (2 years and older) at time of informed consent/assent.
2. Has a clinical diagnosis of AD according to the criteria of Hanifin and Rajka (See [Appendix 2](#)).
3. Has AD involvement of $\geq 5\%$ Treatable BSA (excluding the scalp) at Baseline/Day 1.
4. Has an ISGA score of Mild (2) or Moderate (3) (excluding the scalp) at Baseline/Day 1.
5. Has adequate venous access to permit venipuncture for clinical safety laboratory sampling.
6. Female subjects of childbearing potential who have a negative urine pregnancy test at the screening visit and negative urine pregnancy test at the baseline visit prior to randomization. A female is of childbearing potential if, in the opinion of the investigator, she is biologically capable of having Children (includes any female who has experienced menarche and does not meet the criteria for females not of childbearing potential. Female subjects of non-childbearing potential must meet at least 1 of the following criteria:
 - a. Achieved postmenopausal status, defined as follows: cessation of regular menses for at least 12 consecutive months with no alternative pathological or physiological cause; have a serum follicle stimulating hormone (FSH) level confirming the postmenopausal state;
 - b. Have undergone a documented hysterectomy and/or bilateral oophorectomy;
 - c. Have medically confirmed ovarian failure.
7. Evidence of a personally signed and dated informed consent/assent document indicating that the subject [or parent(s)/legal guardian] has been informed of all pertinent aspects of the study.
8. Willing and able to comply with scheduled visits, treatment plan, laboratory tests and other study procedures.

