9.1. Sample Size Determination

The total sample size of 384 subjects in this study with a 2:1 randomization ratio (256:128) will provide approximately 90% power to detect a 12% difference of percent change from baseline in EASI total score at Day 29 between crisaborole arm and vehicle arm at the 0.05 (2-sided) significance level, CCI

Comparative EASI data relative to vehicle was not collected in previous crisaborole studies. The 12% treatment effect in EASI percent improvement was converted from the ISGA response in the Phase 3 studies using a linear regression equation that evaluated the relationship between ISGA response rate and EASI percent improvement from historical trial

data of other topical products (data on file). From the crisaborole Phase 3 pooled data, the ISGA response rate is 32.1 % for crisaborole and 21.8% for vehicle. The converted EASI percent improvement is 38.9% and 26.8% respectively. The difference of EASI percent improvement between crisaborole and vehicle is approximately 12%.

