5.2. General Methods

5.2.1. Analyses for Binary Endpoints

The binary endpoints will be descriptively summarized using sample size, number, percentage and 95% confidence interval (CI) of percentage at each time point.

Binary data will be analyzed by comparing response rates between treatment groups. Normal approximation to the difference in response rates will be used to obtain p-values and 95% CI.

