6.2.2.1. Main Analysis

- Estimand strategy: Hypothetical.
- Analysis set: FAS. Participants with baseline ISGA score of Clear (0) or Almost Clear (1) will be excluded.
- Analysis methodology: The percentage of subjects achieving Success in ISGA at Day 29 will be compared between crisaborole arm and vehicle arm and the difference will be tested based on normal approximation to response rates.
- Intercurrent events and missing data: Data after treatment discontinuation prior to Day 29 will not be considered. Missing ISGA scores will be derived for the analysis using MI-MCMC.
- Reporting results:
 - Tables: The sample size, number, percentage and 95% CI of percentage of subjects achieving Success in ISGA at Day 29 will be presented for each treatment. Risk difference and the corresponding 95% CI and p-value for the test of difference based on normal approximation to response rates will also be presented at Day 29.

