6.2.4. Success in ISGA and Improvement in ISGA over time

- Analysis set: FAS. Participants with baseline ISGA score of Clear (0) or Almost Clear (1) will be excluded for Success in ISGA.
- Analysis methodology: At Day 8, Day 15, Day 22 and Day 29, the percentage of subjects achieving Success or Improvement in ISGA will be compared between crisaborole arm and vehicle arm and the difference will be tested based on normal approximation to response rates.
- Missing data: Data after treatment discontinuation prior to Day 29 will not be considered. Missing data handling will be the same as in [Section 6.2.1.1](#).
- Reporting results:
 - Tables: The sample size, number, percentage and 95% CI of percentage of subjects achieving Success or Improvement in ISGA at Day 8, Day 15, Day 22 and Day 29 will be presented for each treatment. Risk difference and the corresponding 95% CI and p-values for the test of difference based on normal approximation to response rates will be presented.
 - Figures: For two treatments, line plots of the percentage of subjects achieving Success or Improvement in ISGA and 95% CIs at each post-baseline visit will be displayed graphically

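### Both key secondary ISGA endpoints are tested without the baseline ISGA grade, at some possible cost in precision, and SAP 5.3 step 3 misstates the Success rule

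*SAP*

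**What the plan says.** **The test.** SAP 5.2.1 sets the rule for all binary endpoints: "Normal approximation to the difference in response rates will be used to obtain p-values and 95% CI". SAP 6.2.1.1 applies it to Improvement ("the difference will be tested based on normal approximation to response rates"), and SAP 6.2.2.1 does the same for Success. Protocol 9.2.2 agrees. In SAP 6.2.4 the method is repeated at each visit: "the percentage of subjects achieving Success or Improvement in ISGA will be compared between crisaborole arm and vehicle arm". None of these places names a covariate or a stratum.

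**The baseline grade.** Protocol 4.1, criterion 4, reads: "Has an ISGA score of Mild (2) or Moderate (3) (excluding the scalp) at Baseline/Day 1". For Success, SAP 6.2.2.1 adds: "Participants with baseline ISGA score of Clear (0) or Almost Clear (1) will be excluded". SAP 6.4 already uses baseline ISGA (2 or 3) as a subgroup factor, without p-values. The continuous endpoints carry their baseline value as a covariate (SAP 5.2.2). No stratification factor for randomization is named.

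**The Success rule.** SAP 3.2 and 5.1 and Protocol 9.2.2 define Success as grade 0 or 1 together with an improvement of two grades or more. SAP 5.3 step 3, which derives the variable in every completed data set, asks for grade 0 or 1 together with a change of 2 points. It leaves out *at least* and gives no direction.

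**The concern.** Baseline ISGA is built into both endpoints.

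| Baseline | Improvement (Day 29 grade 0 or 1) | Success (0 or 1, and two or more grades better) |
|---|---|---|
| 2 | one grade or more | must reach 0 |
| 3 | two grades or more | must reach 0 or 1 |

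For Improvement the Day 29 cut-off is the same for everyone, but the distance to it differs. For Success the cut-off itself depends on baseline. A difference in response between the two grades is therefore plausible, though for Success its direction does not follow from the definition. If there is a difference, the crude comparison leaves explainable variance in the standard error.

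These are the first two key secondary tests after EASI, and each must succeed before the Peak Pruritus claim can be tested (SAP 5.1). A precision gain from data already in hand is worth most where power is modest.

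The step 3 wording is a separate matter. It is an operative derivation rule for a gated endpoint, and taken literally it scores the best possible response as a failure.

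**Working it through.** **What the plan states.** No power is given for either ISGA endpoint. The 90% in Protocol 9.1 concerns EASI, and the text after the significance level is blacked out, so it cannot be reproduced. It implies an SD of 12/[(1.960+1.2816)·√(1/128+1/256)] = 34.2. Nothing below depends on it.

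**Inputs from the documents.** n1 = 256, n0 = 128; two-sided 0.05. Protocol 9.1: "the ISGA response rate is 32.1 % for crisaborole and 21.8% for vehicle". These are Success rates: the simple averages of the two pivotal studies in Protocol 1.3.4 are (32.8+31.4)/2 = 32.1% and (25.4+18.0)/2 = 21.7%. For the Asian subgroup, Protocol 1.4.1 has: "with a success in ISGA of 17.3% in the crisaborole group and 11.1% in the vehicle group".

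**Assumptions (not in the documents).** Share w of subjects at ISGA 3: 40–70%. Gap g in response between the two baseline grades: as shown below, in either direction. Common risk difference. Improvement rates of 40% v 30% or 50% v 40%. No missing data.

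**Formulas.**
- Crude variance: V = p1(1−p1)/n1 + p0(1−p0)/n0
- Stratified variance: Vs = V − w(1−w)g²(1/n1+1/n0), with 1/n1+1/n0 = 0.01172
- Power = Φ(d/SE − 1.96)
- With a pooled null SE (SE0): power = Φ((d − 1.96·SE0)/SE)

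**Success at the pooled rates.** d = 0.103.
- V = 0.321·0.679/256 + 0.218·0.782/128 = 0.002183, so SE = 0.04673.
- Unpooled power = Φ(2.204 − 1.96) = 59.7%.
- Pooled: p̄ = 0.2867, SE0 = 0.04895, power = Φ((0.103 − 0.0959)/0.04673) = 56.0%.
- Stratified, w = 0.6, g = 0.25: Vs = 0.002183 − 0.24·0.0625·0.01172 = 0.002007, power = Φ(2.299 − 1.96) = 63.3%.

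**All scenarios** (unpooled power, w from 0.4 to 0.7):

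| Endpoint and rates | Crude | Gap | Stratified | Gain, points |
|---|---|---|---|---|
| Success 32.1 v 21.8 | 59.7% | 0 | 59.7% | 0 |
| | | 10 | 60.1–60.2% | 0.5–0.6 |
| | | 20 | 61.6–62.0% | 2.0–2.4 |
| | | 25 | 62.8–63.4% | 3.1–3.8 |
| Success 17.3 v 11.1 | 39.8% (34.8% pooled) | 10–15 | 40.4–41.5% | 0.6–1.7 |
| Improvement 40 v 30 (assumed) | 50.4% | 20 | 51.9–52.2% | 1.5–1.8 |
| | | 30 | 54.0–54.7% | 3.6–4.3 |
| | | 40 | 57.1–58.6% | 6.7–8.2 |
| Improvement 50 v 40 (assumed) | 46.5% | 20 | 47.8–48.1% | 1.3–1.6 |
| | | 30 | 49.6–50.2% | 3.1–3.7 |
| | | 40 | 52.3–53.5% | 5.8–7.0 |

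For Success at the pooled rates, the variance cut runs from 0 (no gap) to about 8% (25-point gap).

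**Simulation check** of the Mantel-Haenszel risk difference, 200,000 trials per scenario with unstratified 256:128 allocation. Success, w = 0.6, gap 25: 63.2% stratified v 59.6% crude. Improvement 40 v 30, w = 0.5, gap 40: 58.9% v 51.0%. Type I error under the null is 0.050–0.054 for both tests.

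**Step 3.** Among eligible subjects who end at 0 or 1, the two rules can be set side by side:

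| Path | Two grades or more (SAP 3.2, 5.1) | Exactly 2 points (5.3 step 3, literal) |
|---|---|---|
| 2→0 | Success | Success |
| 2→1 | Failure | Failure |
| 3→1 | Success | Success |
| 3→0 | Success | **Failure** |

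The Success rate lost is w × P(clear given baseline 3). Assuming 50–70% at baseline 3 and 3–10% of those clear, it is 0.5·0.03 = 1.5 points to 0.7·0.10 = 7.0 points. Step 3 runs on each completed data set, so observed as well as imputed scores would be affected.

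**The case against.** The strongest case is that nothing in the test is wrong. The crude comparison holds its type I error, matches the declared risk-difference summary, is the same in protocol and SAP, and answers to a randomization for which no stratum is named. The trial is powered for EASI, with no power claimed for ISGA. The gain rests on a baseline split and a response gap that the documents do not give. At a 10-point gap it is about half a point, and moving Success from about 60% to 60–63% does not cure low power.

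The larger figures also need strong inputs. A 40-point gap with Improvement at 40% v 30% and an even split puts vehicle response at 50% in one grade and 10% in the other. At the Asian rates, a 15-point gap favouring ISGA 3 with 70% at ISGA 3 leaves vehicle Success at 11.1 − 0.7·15 = 0.6% in the ISGA 2 stratum, where a normal approximation is doubtful.

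All of that stands as a limit on size. It shows that the change is optional for validity; it does not show that the change is unhelpful. When baseline is not prognostic, stratifying costs essentially no power. It is also fair that SAP 5.3 names neither the imputation variables nor a stratified variance estimator. Those are details to specify and do not undo the proposal.

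On step 3, the correct definition does appear in several other places, so the intent is not in doubt. That makes the correction easy, but the derivation step still contradicts the definition.

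**Conclusion.** Both parts hold. On the test, the crude analysis is valid but leaves out a baseline value that defines the distance to response. For Success at the protocol's pooled rates, stratifying moves power from 59.7% to between 59.7% (no gap) and 63.4% (25-point gap). For Improvement, under assumed rates, the gain is 0 to about 4 points for gaps up to 30 points, and up to 8 at a 40-point gap. These figures assume a common risk difference, 40–70% at ISGA 3 and no missing data. The documents cannot say where in the range the trial lies, and zero is possible. This is an inexpensive improvement that should be made, not the repair of an invalid test.

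On the derivation, SAP 5.3 step 3 is wrong as written and conflicts with SAP 3.2 and 5.1. The only path affected among eligible subjects is 3 to 0, and the intended rule is clear.

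**What to change.** 1. For the ISGA endpoints only (SAP 6.2.1.1, 6.2.2.1 and 6.2.4, their non-responder-imputation and per-protocol versions, and the matching rows of Appendix 1), estimate and test the Mantel-Haenszel risk difference stratified by baseline ISGA, ≤2 v ≥3. These strata give a place to anyone enrolled outside 2–3. The existing exclusion of baseline 0 or 1 for Success stays.
2. Combine over imputations with Rubin's rules as already planned. Name the variance estimator, and state that baseline ISGA is in the imputation model.
3. Keep the crude difference as a sensitivity analysis.
4. Add an exception to SAP 5.2.1 so that EASI-50 and EASI-75 are unchanged.
5. Record the departure from Protocol 9.2.2. Protocol section 9 permits it ("The SAP may modify what is outlined in the protocol where appropriate") and requires an amendment only for major changes to the primary endpoint or its analysis. Make the change before unblinding.
6. In SAP 5.3 step 3, require an improvement of at least two grades from baseline in place of a change of 2 points.

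The cost is SAP wording and a standard procedure option, with no new data. Analysis and reporting become slightly more complex, and there is one documented departure from the protocol.
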